City of Hope National Medical Center and Beckman Research Institute
T: [contact] [name]
Email: [contact]

EXPERIMENTAL DESIGN SCHEMA

PROTOCOL SYNOPSIS

Protocol Title:
A phase I/II dose-escalation trial of leflunomide in patients with relapsed or relapsed/refractory multiple myeloma
Brief Protocol Title for the Lay Public (if applicable):
Leflunomide in relapsed or refractory multiple myeloma
Study Phase:
Phase I/II
Participating Sites:
Single Center: City of Hope, Duarte
Rationale for this Study:
Despite many advances in treatment, multiple myeloma remains an incurable disease and new, effective treatments are needed. Leflunomide is a commercially available oral immunosuppressive agent that has been FDA approved since 1998 for the treatment of rheumatoid arthritis (RA). The primary mechanism of action of leflunomide is inhibition of de novo pyrimidine synthesis by targeting dihydroorotate dehydrogenase (DHODH), and thus achieving anti-proliferative effect in B- and T-lymphocytes. Leflunomide has been investigated for its anti-neoplastic potential in a variety of pre-clinical tumor models. Recent pre-clinical studies have demonstrated significant anti-neoplastic activity in multiple myeloma. In addition, limited clinical experience is suggestive of a beneficial response when leflunomide is used to treat relapsed/refractory multiple myeloma. Considering the favorable toxicity profile and extensive clinical experience with leflunomide in rheumatoid arthritis, this drug represents a potential new candidate for therapy in multiple myeloma.
Objectives:
In patients with relapsed or relapsed/refractory multiple myeloma:
Phase I
Primary Objectives:

○ To determine the maximum tolerated dose (MTD) and recommended phase II dose (RP2D) of leflunomide, when given as a single agent.○ To assess the safety and tolerability of leflunomide at each dose level by evaluation of toxicities including: type, frequency, severity, attribution, time course and duration.
Phase II
Primary Objective:

○ To evaluate the anti-myeloma activity of leflunomide, when given as a single agent, as assessed by overall response rate (ORR).
Secondary Objectives:

○ To obtain estimates of:

- Response duration
- Clinical benefit response
- Overall survival and
- Progression-free survival.

Clinical Pharmacology Objectives (Phase I and II)

- To characterize the relationship between serum concentration of the active leflunomide metabolite, teriflunomide (A77 1726), and toxicity.
- To assess the relationship between serum concentration of the active leflunomide metabolite, teriflunomide A77 1726), and disease response.

Exploratory Ex-Vivo and Molecular Objectives (Phase I and II)

- To explore the relationship between polymorphisms in the *CYP1A2*, *CYP2C19*, or *DHODH* genes and toxicity/response. *CYP1A2*, *CYP2C19* are the hepatic enzymes responsible for leflunomide metabolism.
- To explore the *ex vivo* cytotoxicity of leflunomide toward primary MM cells, in order to evaluate whether individual *ex vivo* leflunomide response might be a useful predictor of therapeutic response.
- To explore the potential additive or synergistic effects of combining leflunomide with other classes of FDA-approved drugs. The classes include HDAC inhibitors, immunomodulatory drugs [IMiDs], proteasome inhibitors, steroid hormones, and antibody therapeutics such as the CD38 antibody daratumumab.
- To generate a preliminary RNA/miRNA and DNA-methylation signature associated with response of MM cells to leflunomide *in vivo* and teriflunomide *ex vivo*.

Study Design:

This study will be conducted as a single center, single agent phase I/II trial.

The phase I portion will implement a modified rolling six dose escalation design, a more conservative version of the rolling six design of Skolnik, et al. [1], for enrollment with dose escalation, de-escalation, or expansion of a cohort on the basis of the occurrence of dose limiting toxicities (DLTs) during cycle 1.

The starting dose of leflunomide is 20mg daily, with the intention to test up to 60mg daily. Escalation will proceed in increments of 20mg/day (odd numbered dose levels); de-escalation will proceed in decrements of 10mg/day. Up to six doses of leflunomide will be considered:

Dose Level	Leflunomide Dose*
-1	10 mg PO daily
1	20 mg PO daily
2	30 mg PO daily
3	40 mg PO daily
4	50 mg PO daily
5	60 mg PO daily

*NOTE: Leflunomide is administered with a loading dose of 100 mg for the 1st three doses.

The highest dose level that produces $\leq 1/6$ DLTs in cycle 1 will be the MTD. The RP2D of leflunomide will generally be the MTD, but it may be less than the MTD based on a review of available data/cumulative toxicities.

Following the phase I trial, a single arm phase II trial will be conducted using a Simon Two-Stage Optimal Design [2, 3] to evaluate the anti-myeloma activity of leflunomide, when given as a single agent, as assessed by overall response rate (ORR). The phase II portion of the study is expected to enroll a minimum of 19 and a maximum of 39 patients. The sample size is based on the desire to discriminate a promising ORR of 30% from a disappointing response rate of 15% using a type I error rate of 0.10 and power of 80%.

Patients will be treated in planned 28-day treatment cycles until disease progression, unacceptable toxicity, or other criteria for removal from study treatment are satisfied. Patients will undergo monthly evaluation for response using the International Myeloma Working Group (IMWG) criteria.

Endpoints:

Phase I: The primary endpoint is toxicity. Toxicity will be graded according to the NCI-Common Terminology Criteria for Adverse Events version 4.03. Dose limiting toxicity (DLT) is defined in [Section 13.1](#) of the protocol.

Phase II: The primary endpoint is response. Response will be categorized using the IMWG response criteria for multiple myeloma [37, 38]. The response categories and criteria are summarized in Table 11.2 of the protocol.

Sample Size:

The expected phase I sample size is 12-18 patients; allowing for 6 patients to replace invaluable/ineligible patients. The expected phase II sample size is 19-39 patients. It is anticipated that the 6 patients from the phase I portion who are treated at the R2PD will be included in the sample size for the phase II portion (phase I/II participants).

Estimated Duration of the Study

With an expected accrual rate of approximately 1 patient enrolled per month, the phase I portion of the trial is expected to complete accrual in 12-18 months. The phase II portion is expected to accrue 2 patients per month, with completion in 17 months. The expected maximum duration of therapy is 24 months. The total study is expected to last a maximum of (18+17+24) 59 months or approximately 5 years.

Summary of Subject Eligibility Criteria:

Inclusion Criteria:

Participants must meet the following criteria on screening examination to be eligible to participate in the study:

- All subjects must have the ability to understand and the willingness to sign a written informed consent.
- Patients must be age ≥ 18 years.
- Patients must have a life expectancy of > 3 months.
- Patients must exhibit an ECOG performance status of 0-2.
- Patients must have a diagnosis of multiple myeloma.
- Patients must have measurable disease, defined as one of the following within 21 days prior to registration:
 - Serum M-protein ≥ 0.5 g/dL
 - Urine M-protein ≥ 200 mg/24 hr

- Serum free light chain ≥ 10 mg/dL provided the FLC ratio is abnormal.
 - 10% plasma cells in bone marrow
- Patients must be relapsed or are refractory to at least 3 prior lines of therapy, including both a proteasome inhibitor and an IMiD, and for whom transplant is not recommended (induction therapy and stem cell transplant +/- maintenance will be considered as one regimen).
- At least 2 weeks from prior therapy to time of start of treatment. Prior therapy includes steroids (except prednisone or equivalent – up to 10 mg per day is allowed).
- Platelet count $\geq 50,000/\mu\text{L}$. Platelet transfusions are not allowed within 14 days of platelet assessment.
- ANC $\geq 1000/\text{mm}^3$. Growth factor is not permitted within 14 days of neutrophil assessment.
- AST and ALT $< 2.0 \times \text{ULN}$.
- Total Bilirubin $< 1.5 \times \text{ULN}$.
- Calculated creatinine clearance (CrCl) $\geq 30 \text{ mL/min}$ per 24-hour urine collection or the Cockcroft-Gault formula.
- Negative serum or urine β -HCG test (female patient of childbearing potential* only), to be performed locally within the screening period.
- Negative for tuberculosis antigen (e.g. T-Spot test).
- Negative for hepatitis A, B, or C infection.
- Adequate pulmonary function as defined by FVC and DLCO $\geq 50\%$ of predicted by pulmonary function testing.
- Agreement by females of childbearing potential* and sexually active males to use an effective method of contraception (hormonal or barrier method of birth control or abstinence) prior to study entry and for three months following duration of study participation. The effects of study treatment on a developing fetus have the potential for teratogenic or abortifacient effects. Should a woman become pregnant or suspect that she is pregnant while participating on the trial, she should inform her treating physician immediately. *A female of childbearing potential is defined as a sexually mature woman who: 1) has not undergone a hysterectomy or bilateral oophorectomy; or 2) has not been naturally postmenopausal for at least 24 consecutive months.

Exclusion Criteria

Prospective participants who meet any of the following criteria will not be eligible for admission into the study:

- Prior treatment with leflunomide.
- Current or planned use of other investigational agents, or concurrent biological, chemotherapy, or radiation therapy during the study treatment period. (See inclusion criterion #8 for washout times).
- Current or planned growth factor or transfusion support until after initiation of treatment. If growth factor or transfusion support is provided between screening and start of treatment, the participant will no longer be eligible.
- Prior diagnosis of rheumatoid arthritis.
- Prior Allogeneic transplant.
- Acute active infection requiring systemic therapy within 2 weeks prior to enrollment.
- Pre-existing liver disease.
- Known HIV infection.
- History of allergic reactions attributed to compounds of similar chemical or biologic

composition to leflunomide or cholestyramine.
 
• Non-hematologic malignancy within the past 3 years aside from the following exceptions:
○ adequately treated basal cell or squamous cell skin cancer○ carcinoma in situ of the cervix○ prostate cancer < Gleason Grade 6 with a stable PSA○ successfully treated in situ carcinoma of the breast• Clinically significant medical disease or condition that, in the investigator's opinion, may interfere with protocol adherence or the patient's ability to give informed consent.• Pregnant women and women who are lactating. Leflunomide has potential for teratogenic or abortifacient effects. Because there is a potential risk for adverse events in nursing infants secondary to treatment of the mother with these agents, breastfeeding should be discontinued if the mother is enrolled on this study.• Any other condition that would, in the Investigator's judgment, contraindicate the patient's participation in the clinical study due to safety concerns or compliance with clinical study procedures, e.g., infection/inflammation, intestinal obstruction, unable to swallow medication, social/ psychological issues, etc.• Prospective participants who, in the opinion of the investigator, may not be able to comply with all study procedures (including compliance issues related to feasibility/logistics).

Investigational Product Dosage and Administration:


Leflunomide will be administered orally at an initial dose of 20 mg daily following a loading dose of 100 mg per day for the first three days of administration. For the phase I portion of the study, five daily dose levels of leflunomide may be tested (10, 20, 30, 40 or 60 mg daily) There will be no intra-patient dose escalation. The R2PD will be used as the daily dose for the phase II portion of the study. At the end of the study, all participants will receive 11 days of oral cholestyramine treatment (8 g three times daily) to reduce the plasma leflunomide levels.

Clinical Observations and Tests to be Performed:
 
Clinical observations will include tolerance as well as response to treatment. Baseline studies will include: history and physical, pulmonary function test, skeletal survey and bone marrow aspiration and biopsy (the bone marrow aspiration will be used for clinical assessment and leftover samples will be used for correlative laboratory studies), as well as a laboratory evaluation to include CBC with differential, comprehensive chemistry panel (to include LDH, magnesium, phosphorus and uric acid) and myeloma labs (serum protein electrophoresis, serum immunofixation, 24-hour urine protein electrophoresis, urine immunofixation, serum free light chains, and quantitative immunoglobulins). Clinical observation of response will take place on day 1 of each 28-day cycle. Subjects will be evaluated through clinic visits and physical exams as well as laboratory tests to include CBC with differential, comprehensive chemistry panel and myeloma labs. Blood tests will be performed at a minimum of every 28 days but may be done more frequently as clinically indicated. A skeletal survey may be repeated as clinically indicated. Patients will undergo toxicity assessment every two weeks for the first three cycles following initiation with leflunomide and will undergo, at a minimum, monthly toxicity assessments thereafter. For all phase II patients and phase I patients enrolled at the anticipated RP2D, a second bone marrow aspiration will be conducted for correlative laboratory studies on day 1 of cycle 2. Confirmation of complete response (CR), stringent complete response (sCR), and progressive disease (PD) will involve bone marrow aspiration and, for patients who have enrolled in the phase II portion, leftover samples from these bone marrow aspirations will be used

for correlative laboratory studies.
Statistical Considerations:

Analysis: Observed toxicities will be summarized in terms of type (organ affected or laboratory determination), severity, attribution, time of onset, duration, serum concentration of the active leflunomide metabolite, probable association with the study treatment and reversibility or outcome. Baseline information (e.g. the extent/type of prior therapy) and demographic information will be presented as well to describe the patients treated in this study.
 
Rates and 95% Clopper Pearson binomial confidence interval (CI) will be calculated for overall response rate (patients that have confirmed sCR/CR/VGPR or PR) and clinical benefit rate (patients that have confirmed sCR/CR/VGPR/PR/MR or SD). In addition, sub-analyses will be performed where participants will be considered evaluable for response if they are confirmed eligible, receive at least 75% of leflunomide during the first cycle of therapy and have their disease re-evaluated. Response rates will also be explored based on number/type of prior therapy(ies) and serum concentration of the leflunomide metabolite (μg/mL). Time to response and survival will be estimated using the product-limit method of Kaplan and Meier.
 
Serum trough levels of leflunomide's active metabolite, teriflunomide (A77 1726), will be measured in each patient at multiple time points throughout the study. Both total and free teriflunomide will be tested. The association between serum levels and toxicity, as well as response, will be evaluated at the conclusion of the study.
 
Genetic polymorphisms in genes associated with the biological activity of leflunomide (e.g., DHODH, CYP1A2, and CYP2C19) have been previously described and will be explored for possible associations with response and safety outcomes.
 
Ex vivo studies will be performed on bone marrow aspirate-derived cells to evaluate the IC50 for teriflunomide and the potential synergy with other anti-neoplastic agents. Correlation analyses will be performed to determine the relationship between ex vivo and in vivo response.
 
Preliminary molecular profiles for miRNA, mRNA, and DNA methylation status will be derived from both ex vivo and in vivo treatment. These profiles will be used to identify molecular correlates of therapeutic response using pathway identification and supervised principal components analysis.

Sponsor/Licensee:
Investigator Initiated: City of Hope
Case Report Forms

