9.4.2 Sample Storage and Distribution for Further Analysis

At least 5 million ($\geq 5\%$) CD138-positive MNCs can be expected from each BM aspiration after immunomagnetic enrichment. For RNA and DNA analysis without further ex vivo treatment, 500,000 cells (RNA) and 1,000,000 cells (DNA) will be pelleted and frozen at -80°C . The remaining CD138-enriched cells will be stored in the vapor phase of a liquid nitrogen tank in freezing medium if the cells are not processed immediately. A small aliquot of the cell population ($\sim 50,000$ cells) will also be used to confirm that the enriched cell population is $>95\%$ pure. Up to three million CD138-enriched cells will be

used for *ex vivo* cell culture studies either immediately after enrichment or after thawing of the frozen cells. See Table 9.3.2 for allocation of samples to downstream assays. If insufficient cell numbers are collected for the proposed *ex vivo* and molecular studies, we will prioritize as follows: mRNASeq/miRNASeq > *ex vivo* cytotoxicity studies > DNA methylation sequencing studies > *ex vivo* synergy studies.

Table 9.3.2 Distribution of CD138-enriched bone marrow aspirate cells for research

	Ex vivo teriflunomide or control treatment			No ex vivo treatment
	Cytotoxicity	Synergy analysis	mRNA/miRNA profiling	mRNA/miRNA/DNA methylation profiling
Baseline/screening	X**	X**	X***	X***
1 mo. of leflunomide				X***
Progression*				X***
Complete response*				X***

*Where applicable, ** both the phase I and phase II components, *** all participants treated at the R2PD (phase II and phase I/II participants)

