For the studies combining teriflunomide with other agents *ex vivo*, combination Index (CI) values will be calculated using the CalcuSyn software program (Biosoft, Ferguson) to determine which of the compounds work synergistically, if any. A combination index of < 0.9 indicates synergism, whereas $CI = 0.9$ to 1.1 indicates additive effects. $CI > 1.1$ indicates antagonism. Isobogram diagrams will be generated that show the varying combination treatments and the ratio where maximal synergy is obtained.

The miRNA/mRNA expression profile and DNA methylation data will be used to identify the miRNA/mRNA and differential methylated regions (DMRs) that show significant differences between responders and non-responders after leflunomide treatment. For miRNA/RNA profiling, fold changes >3 with an FDR <0.05 will be considered significant. Assuming the dispersion of genes across replicates is 0.2 and minimum average expression is 10 reads per gene, 10 samples in each group (responder vs. non-responder) should have 89% power to detect a 3-fold difference between groups at an FDR level of 0.05.

The major goal of RNA-seq/miRNA-seq/RRBS-seq is to predict potential responders based on pre-treatment genomic profiling. A logistic regression-based algorithm with risk score formula described previously [46] will be used to build a classifier for response prediction. Differentially expressed miRNA/mRNA and DMRs together with other known clinical risk factors will be included in the

multivariable logistic regression model. The performance of the identified classifier will be evaluated with leave one out cross validation (LOOCV). Specifically, for each iteration -as part of a random selection process, one sample will be left out as the test sample; the remaining samples will be used to build a classifier, and the classifier will be used to predict the response status of the test sample. The sensitivity and specificity of the classifier will be calculated, as well as receiver operating characteristic (ROC) curve and area under the curve (AUC) to evaluate its accuracy.

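### The synopsis names supervised principal components for the molecular correlates, but section 13.5 describes a multivariable logistic classifier with no stated penalty, reduction step or predictor cap, which is likely to have no finite estimate once about three strong features enter

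*Combined protocol and SAP*

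**What the plan says.** The Protocol Synopsis, under Statistical Considerations, says of the miRNA, mRNA and methylation profiles: "These profiles will be used to identify molecular correlates of therapeutic response using pathway identification and supervised principal components analysis". Pathway identification is carried into section 13.5 and Appendix B. Supervised principal components is not mentioned in either.

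Section 13.5 (Ex vivo and molecular studies) gives prediction of responders from pre-treatment profiles as the major goal of the sequencing. Its method is this: "A logistic regression-based algorithm with risk score formula described previously [46] will be used to build a classifier for response prediction". It continues: "Differentially expressed miRNA/mRNA and DMRs together with other known clinical risk factors will be included in the" multivariable logistic model. Performance is to be judged by leave-one-out cross-validation, with sensitivity, specificity and ROC area.

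The selection rule for miRNA and RNA is "fold changes >3 with an FDR <0.05 will be considered significant". No threshold is given for methylated regions. The power statement is that "10 samples in each group (responder vs. non-responder) should have 89% power to detect a 3-fold difference between groups", under these conditions: "Assuming the dispersion of genes across replicates is 0.2 and minimum average expression is 10 reads per gene".

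Table 9.3.2 in section 9.4.2 limits this profiling to participants treated at the RP2D. The phase II design in section 13.3 caps that group at 39.

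**The concern.** Two places in one document name different methods for relating the profiles to response, and the method in the synopsis is never specified. The method in section 13.5 is also fragile at this sample size. Features are chosen because they differ strongly between responders and non-responders. If several such features enter a logistic model fitted by plain maximum likelihood to 39 patients or fewer, some combination of them may split the two groups perfectly. The likelihood then has no maximum at finite coefficients. The reported weights depend on where the software stops iterating, fitted probabilities go to 0 or 1, and the adjustment for clinical factors has no useful meaning. The model is most likely to fail in this way when the profiling has found real signal.

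**Working it through.** **Inputs from the documents.** Phase II: 19 patients in stage 1, stopping at 3 or fewer responses, then 20 more; response rates 15% and 30% (section 13.3). Profiling: 3-fold difference, dispersion 0.2, mean of 10 reads, 10 per group, 89% power (section 13.5).

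**The plan's own figures.**
- The exact binomial probability of 3 or fewer responses in 19 at 15% is 0.684, which matches the stated 0.68. The attained type I error is 0.097 and the power 0.803.
- For the RNA power, the variance of the log fold change is (1/mu + dispersion)(1/n1 + 1/n2) = (0.1 + 0.2)(0.1 + 0.1) = 0.06, so the standard error is 0.245. Then ln 3 / 0.245 = 1.099 / 0.245 = 4.49. With a two-sided per-gene alpha of 0.001 (z = 3.29), power is Phi(4.49 - 3.29), or 88.4%. The stated 89% corresponds to an alpha of about 0.0011. The plan does not say how its FDR level maps to a per-gene alpha.

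**Responders available.** In a full trial, 39 x 0.15 = 5.85 and 39 x 0.30 = 11.7, hence about 6 to 12. If the trial stops at stage 1, there are at most 3 responders among 19.

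**Size of a 3-fold difference.** With means of 10 and 30 reads, the log-scale variances are about 1/10 + 0.2 = 0.300 and 1/30 + 0.2 = 0.233. Their average is 0.267, an SD of 0.516. So ln 3 / 0.516 = 2.1 SD by this approximation; simulated on log2(count + 1) it is about 2.0 SD. For k independent features, the best linear combination separates the group means by 2.0 x sqrt(k) SD: 2.8 for two, 3.5 for three, 4.0 for four. That is why separation rises so quickly.

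**Separation check.** Negative-binomial counts (means 10 and 30, dispersion 0.2) were simulated for 39 patients with 6 to 12 responders and independent genes. Complete separation was tested by linear programming.

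| Features in model | Fits with no finite estimate |
|---|---|
| 1 | 2-10% |
| 2 | 34-54% |
| 3 | 78-87% |
| 4 | 98-100% |
| 5 | 100% |

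Separate runs of 400 agree within a few points (30-56% with two, 78-90% with three, 97% or more with four).

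**Sensitivity to assumptions.**
- Correlation 0.3 between features: 82% (12 responders) to 94% (6 responders) with five features, 99-100% with eight.
- Correlation 0.5: 59-82% with five, 88-98% with eight.
- Weaker independent signals (1.5 SD): 22-41% with three, 88-93% with five, 99-100% with eight or more.
- Pure-noise predictors: 0% with up to five, 82-100% with twenty.

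**Prediction in new patients.** This was simulated with 5,000 features and the plan's selection rule, 40 runs per setting. Feature spread, number of true signals and correlation are assumptions that the documents do not give. Areas under the ROC curve are for unpenalised logistic regression on all selected features against the first supervised component.
- Median of 1-2 features selected: 0.87 v 0.88, 0.91 v 0.91 and 0.94 v 0.95 (6, 9 and 12 responders).
- Many correlated features selected (medians about 27 to 85): 0.58-0.65 v 0.92. A single weighted risk score reached 0.91-0.92 in the same setting.
- Independent strong signals, median of 8 or 11 selected: 97-100% of fits separated, yet the areas were 0.99 v 0.99 and 1.00 v 1.00. Separation destroys coefficients and probabilities, but it does not always destroy ranking.

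**The case against.** The strongest reply is that section 13.5 does not describe the model being criticised. It does not say that all selected features enter, nor that the regression is unpenalised. It points to a published risk-score formula, and the cited title concerns a four-microRNA signature, which suggests a short list that may be collapsed into one score. Such a score predicted as well as the principal component in the simulation. This stands in part: the cited source is outside the documents, so a reduction step cannot be ruled out. But the formula is not written out, and section 13.5 also places the features in a multivariable model. If the score's weights come from that joint fit, they inherit its separation.

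A second reply is that the synopsis speaks of identifying correlates, whereas section 13.5 builds a classifier, so the two need not conflict. That is fair as to wording. It still leaves supervised principal components promised and never specified.

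A third is that the range of 6 to 12 responders assumes a full trial. At a 15% response rate the trial stops early with probability 0.68. The expected size is then 19 + 20 x (1 - 0.684) = 25.3 patients, with 3.8 responders. This is correct, and with 3 or fewer responders the change proposed here would not rescue a classifier either.

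Finally, the aim is listed as exploratory and the signature as preliminary. That limits the severity.

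**Conclusion.** The point holds in a limited form. The synopsis and section 13.5 name different methods. The one in section 13.5, read without a penalty or reduction step, is likely to have no finite estimate once about three features of the size the plan targets enter together. The percentages rest on true 3-fold differences, dispersion 0.2, 10 reads, independent genes and 39 patients; correlated or weaker features need a larger number to reach the same rate.

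A reader might infer more than this. That the model can never be estimated with 6 to 12 responders is not supported: the outcome depends on how many features enter, and with one feature a finite estimate usually exists. That every feature will enter an ordinary logistic model is an inference from silence. That the classifier will predict worse by some fixed amount is not supported either: the loss runs from negligible with one or two features to large with many correlated ones, and the documents do not fix which case applies.

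The response-rate analysis, the safety analysis and the phase II decision rules are unaffected. This is a low-severity point, worth acting on because the change costs almost nothing.

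**What to change.** In section 13.5, replace the sentence that enters the selected features jointly in the logistic model with the following:

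- Reduce the selected features to a single score. This can be the first supervised principal component, as the synopsis has it, or a risk score written out in full whose weights do not come from the joint unpenalised fit.
- Enter that score with at most one or two clinical factors, named in advance, in a penalised (Firth or ridge) logistic model.
- State that feature selection, scoring and fitting are all repeated within every leave-one-out fold.
- Give the same method in the synopsis.

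The cost is a few lines of wording and standard R code, with no new data or samples. The downside is that there is no separate adjusted coefficient for each gene; component loadings or score weights can be reported instead.
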